Protocol

JIA (Juvenile Idiopathic Arthritis) Toolbox Feasibility Study

JIA Toolbox Feasibility Study

18/12/2024 Version 2

IRAS number: 336429

The undersigned confirm that the following protocol has been agreed and accepted and that the Chief Investigator agrees to conduct the study in compliance with the approved protocol and will adhere to the principles outlined in the Declaration of Helsinki, the Sponsor's SOPs, and other regulatory requirement.

I agree to ensure that the confidential information contained in this document will not be used for any other purpose other than the evaluation or conduct of the investigation without the prior written consent of the Sponsor

I also confirm that I will make the findings of the study publicly available through publication or other dissemination tools without any unnecessary delay and that an honest accurate and transparent account of the study will be given; and that any discrepancies from the study as planned in this protocol will be explained.

KEY STUDY CONTACTS

Chief Investigator	[name] (Design Researcher at SHU), [contact] [name]
Sponsor	[name], [contact] , [name]
Funder(s)	Medical Research Council (MRC IAA 2023 Call)
Co-Investigator	[name] (Consultant Paediatric Rheumatologist at SCH), [contact] , [name]
Co-Investigator	[name] (Occupational Therapist at SCH), [contact]
Co-Investigator	[name] (Principal Research Fellow at SHU), [contact] , [name]
Co-Investigator	[name] (Researcher and product designer at SHU) [contact]
Advisor	[name] (Director of Juvenile Arthritis Research (JAR) charity)

STUDY SUMMARY

Study Title	JIA Toolbox Feasibility Study
Internal ref. no. (or short title)	JIA Toolbox Feasibility Study
Study Participants	Children with JIA (aged 7-16), their parents and their teachers
Planned Size of Sample (if applicable)	N=25
Planned Study Period	9 months (08.04.24 – 31.07.25)
Research Question/Aim(s)	
What are the potential impacts of using 'JIA Toolbox' for:
 
 - Children and Young People (CYP) with Juvenile Idiopathic Arthritic (JIA) in terms of improving overall condition management by enabling independence and improved functional ability? - Parents of CYP with JIA in terms of enabling improved condition management? - Healthcare Professionals (HCP's) working in JIA management in terms of improving physio adherence? - and teachers of children with JIA in terms of improving communication around the condition in the classroom?

The Research Team and expertise:

CI: [name] – Design Researcher and Product Designer. Expertise in co-designing technological healthcare solutions and delivering multiple healthcare research projects.

CO-I: [name] – Consultant Paediatric Rheumatologist. Expertise in treating and managing Juvenile Idiopathic Arthritis and delivering healthcare research projects.

CO-I: [name] – Specialist Paediatric Rheumatology Occupational Therapist. Expertise in working with children with JIA on their occupational needs and therefore areas of difficulty that are unmet by current products and delivering healthcare research projects.

CO-I: [name] – Industrial Designer and design researcher. Expertise in designing and prototyping products for industry, including electronic, sensor and textile-based solutions, and delivering a variety of health related research projects.

CO-I: [name] – Principal Research Fellow. Expertise in design and co-design as methods of applied Research and Knowledge Mobilisation in the field of Health and Wellbeing.

The team is highly experienced in:

- Translational research,
- Patient focused research,
- Co-designing solutions,
- Developing products, services and interventions that promote dignity and enhance quality of life,
- And commercialisation of solutions – example ‘head-up’ neck collar (designed, developed and currently on the market) and recently awarded global ‘Made With Patients’ award.

Protocol

1.0 Lay Summary

This is a 12-month feasibility study to test the effectiveness and viability of a group of 3 assistive devices to help improve independence and functional ability for children and young people (CYP) with Juvenile Idiopathic Arthritis (JIA). These devices have been extensively co-designed with CYP with JIA, their parents, healthcare professionals and teachers, ensuring they provide solutions to priority unmet needs within the JIA community. The devices have already undergone a successful proof-of-concept study. This feasibility project aims to assess the effectiveness and viability of the devices in a real-world setting over a longer time-frame and with a larger cohort.

2.0 Background

This study aims to assess the potential impacts of ‘JIA Toolbox’, (Appendix1) – three novel prototypes that collectively aim to improve the independence and functional ability of Children and Young People (CYP) with Juvenile Idiopathic Arthritis (JIA).

‘JIA Toolbox’ addresses key unmet needs identified by stakeholders during previous work. Each prototype (Appendix1) addresses a specific unmet need:

UNMET NEED: Joint pain that prevents CYP from doing activities they love.

PROTOTYPE 1 SOLUTION: a wearable pain management device that heats and vibrates to help distract the brain from pain based on the idea of gate theory.

UNMET NEED: CYP don't engage with their physio as they find it boring and frustrating due to perceived lack of progress. This therefore creates ongoing strained and frustrated relationships with parents and HCP's.

PROTOTYPE 2 SOLUTION: a motivational physiotherapy tool that incrementally lights up in response to the stretches helping CYP visualise and 'see' progress.

UNMET NEED: CYP often need help in the classroom but are too embarrassed to put their hand up as they don't want everyone to know about their condition. This can lead to feelings of disbelief from the teacher and a strained relationship between pupil and teacher.

PROTOTYPE 3 SOLUTION: a communication wearable for school that silently vibrates to alert the teacher to difficulty enabling better communication and combatting feelings of disbelief.

Our previous proof-of-concept study received positive feedback, prompting the drive to refine the prototypes and continue with a feasibility study. Our work aims to improve outcomes for CYP with JIA by empowering and equipping them: to self-manage confidently and independently, to harness their wider support network when necessary and to embed positive health behaviours from a young age.

1,000-1,500 CYP are diagnosed with JIA every year [2]. It affects CYP's lives, "impacting on relationships, school, physical and individual domains" [4] due to "chronic or recurrent pain and disability" [3]. Widespread lack of understanding often makes CYP with JIA feel isolated, e.g. "There will always be a teacher who responds to me being tired, with: 'I also get tired, but still got to do stuff'" [6]. There are products designed to support CYP with JIA but they have limitations and our previous work shows they are not sensitive to user needs. 'JIA Toolbox' has been developed using a co-design approach with CYP, parents/guardians, HCPs and teachers to ensure that it meets key stakeholder needs and is therefore more likely to be adopted by patients and clinical services.

A major priority for health services is helping people with long-term conditions (LTC's), including arthritis, as highlighted in the 2030 Agenda for Sustainable Development. LTC's such as JIA can be life-limiting with emotionally and physically debilitating effects. Longer term, JIA can restrict access to employment, putting increased pressure on the economy and healthcare resources. Developing self-management skills from a young age is crucial to managing chronic illness. Equipping CYP to become confident in managing their own condition is particularly important as CYP transition from children's to adults' services.

COVID-19 highlighted the importance of effective self-management as healthcare resources were diverted to support COVID-19. This withdrawal of, or limited access to, key support can have a negative impact on the physical and mental wellbeing of CYP with LTC's. The development of self-management tools such as 'JIA Toolbox' is key to help relieve pressure on healthcare professionals and alleviate concerns of patients. The wider, informal stakeholder support networks surrounding each patient such as teachers are also

an integral part of condition management. However, they remain an under used resource. In part, this is due to the lack of appropriate resources (tools, knowledge, information, power) to support CYP in seeking help from such people and in part, due to a lack of appropriate resources (tools, knowledge, information, empathy) that enable these people to provide relevant kinds of support. The tools in 'JIA Toolbox' aim to fill this gap. This is novel, relevant and potentially transferrable to other chronic conditions.

Existing studies describing the experience of living with JIA [3-6] tend to focus exclusively on one stakeholder's experience or on the physical symptoms, neglecting both the wider life impact and insights of other stakeholders. This study will therefore provide contemporary data on CYPs experiences of living with JIA to inform future research.

3.0 Clinical need

Juvenile Idiopathic Arthritis (JIA) is a paediatric long-term condition affecting approximately 15,000 children and young people (CYP) in the UK, with 1,000-1,5000 new diagnoses each year. It causes ongoing joint inflammation, pain and stiffness, making everyday activities difficult. It affects every aspect of CYP's lives, impacting on physical, social, emotional and education development, with widespread lack of understanding often making CYP with JIA feel isolated. There are products designed to support CYP with JIA but they have limitations and our previous work (a survey and co-design process conducted in 2018) shows they are not sensitive to user needs. Our survey highlighted that CYP with JIA find these products difficult to use as most therapeutic aids are targeted towards an adult population. The few that are aimed at children were seen as patronising and stigmatising. These products also often neglect to take into account the wider stakeholder network such as parents, teachers and healthcare professionals, and therefore neglects to support them in helping CYP with JIA.

Key stakeholder groups (CYP with JIA, their parents, healthcare professionals and teachers) were active participants throughout our previous work, through co-design workshops and surveys. The key highlighted clinical need was assistance with self-management.

This is broken down into the following specific unmet needs:

- Pain-management. Improved pain management would enable CYP to do more of the things they love, by providing a solution that they can use independently as and when is needed, positively impacting their wellbeing.
- Physiotherapy adherence as currently CYP often do not do clinician-recommended exercises. Improved compliance with recommended physiotherapy interventions may reduce pain in the long-term and improve mobility.
- Communication between the pupil and teacher. Improving this communication would provide CYP with a way to discreetly access necessary support without facing stigma, improving their concentration by removing anxiety around accessing help

As a result, 'JIA Toolbox' was co-designed and developed to fulfil these needs and previously tested on a cohort of n=10 CYP with JIA during a proof-of-concept study. The results from

the proof-of-concept study were successful with 80% of participants finding one or more of the prototypes beneficial for their condition management.

The aim of this study is therefore to further refine the prototypes based on participant feedback and then test their effectiveness and viability over a longer time frame (3 months) with a larger cohort (n=25) in improving overall condition management in terms of improved independence and functional ability. The data collected will therefore be: experiences of living with JIA both with and without 'JIA Toolbox' and prototype use patterns to build up a strong evidence based on the effectiveness and viability of these devices, enabling a good point from which to leverage further funding.

4.0 Study Objectives and Purpose

This is a feasibility study assessing the effectiveness and viability of Juvenile Idiopathic Arthritis (JIA) Toolbox in improving overall condition management by improving Children and Young People's (CYP's) independence and functional ability.

Each prototype was developed to address an unmet need and therefore has a specific aim:

- Prototype 1: A wearable device that aims to promote pain self-management skills;
- Prototype 2: A motivational tool that aims to improve physiotherapy engagement;
- Prototype 3: A wearable device that aims to promote discrete communication between CYP and teachers and other stakeholders.

The primary objective of this study is to explore the potential impact of 'JIA Toolbox' in addressing the unmet needs identified by stakeholders by conducting a feasibility study to explore the usage of the three prototypes and their impact on CYP's independence and functional ability.

The secondary objective is to collect contemporary data on CYP's experiences of living with JIA to inform future research and innovation.

5.0 Study Design

CYP aged 7-16 years with JIA, parents/guardians and HCPs based at Sheffield Children's Hospital (SCH) and/or a part of Juvenile Arthritis Research (JAR) charity will participate throughout this study.

The components of 'JIA Toolbox' are illustrated in Appendix 1. The potential impact of these devices will be assessed by comparing baseline qualitative data about living with JIA, with data collected when the devices are in use. Post-intervention interviews with participants will capture practical usability issues and the potential impact of 'JIA Toolbox' on CYP's wider life, like social impact, to frame possible outcome measures for future evaluation.

The study design is shown in Appendix 2. It will consist of:

WP4

4.1 Recruitment of participants n=25 (CYP aged 7-16) and their parents/guardian from SCH or JAR

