5.1 Prototype testing by clinical engineering

5.2 Virtual training session on data collection processes for participants (1 hour)

5.3 Baseline data collection period (2 weeks)

5.4 In person training session on prototypes (1- 1.5 hours)

5.5 Intervention period using prototypes (3 months)

5.6 'JIA Toolbox' returned to SCH

5.7 post-intervention data collection period (2 weeks)

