5.8 End of intervention interview (1 hour 1:1 with researcher)

WP6

6.1 Analyse qualitative data with healthcare professionals who are a part of the research team

The end of study is defined as the date of the last interview of the last participant.

As 'JIA Toolbox' consists of therapeutic self-management tools, participants will decide when to use the prototypes during the 3-month intervention period. As such, there should be no added burden to the participants in using these products, as they are designed to assist with condition management rather than hinder. There will be two training sessions, one on how to use the data collection packs (examples shown in appendix 3) and one on how to use the prototypes. This will ensure that the participants are clear on what they should do, minimising any potential risks in interacting with the prototypes. There will be regular weekly check ins to ensure participants are happy with the study and to troubleshoot any issues raised. The 3-month intervention period where the participants are using the devices will take place over August, September and October, giving CYP 1 month to get used to the devices prior to using them in a school context. From the previous proof-of-concept study, it was highlighted that the devices were beneficial in building CYP-teacher relationship near the beginning of the school year. Post-intervention interviews will be conducted at the end of the study to ensure all experiences are equally captured and to give participants the opportunity to highlight anything they feel needs additional clarification.

The study design has had input from YOUR RHEUM which is a group of CYP (11-24) with diagnosed rheumatic conditions, and JAR which is a group of CYP (7-25) with Juvenile Arthritis. Both groups regularly input on CYP rheumatology research. They have a strong track-record in advising on and shaping rheumatology research and represent a 'Gold Standard' approach to PPI involvement. These groups have been involved in shaping the study design and participant facing materials such as the data collection packs to ensure they are appropriate and will be effective. They have also commented on the prototypes themselves, feeling that they fulfill key unmet needs within the JIA population. [name] and [name] are both healthcare professionals who work within

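### Impact is to be judged on data collected while the devices are in use, but the listed schedule places its data collection before first use and after return

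*Protocol*

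**What the plan says.** The protocol makes three statements about in-use data.

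- Section 5.0 (Study Design): impact will be assessed by "comparing baseline qualitative data about living with JIA, with data collected when the devices are in use".
- Section 3.0 (Clinical need), closing paragraph: the data will cover living with JIA with the Toolbox and without it, together with "prototype use patterns to build up a strong evidence based on the effectiveness and viability of these devices".
- Section 15.0 (Outcomes), second output: detailed data on symptoms and on how the prototypes are used, from 25 children over three months.

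Section 5.0 then sets out the steps. The relevant ones, in listed order, are:

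- first, "5.3 Baseline data collection period (2 weeks");
- a face-to-face session that teaches families to use the devices (step 5.4);
- three months of use at the child's own discretion (step 5.5);
- hand-back of the devices to the hospital (step 5.6);
- only then, "5.7 post-intervention data collection period (2 weeks");
- last, an individual interview lasting an hour (step 5.8).

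Two other parts of section 5.0 bear on the point. Weekly check-ins are planned, and their purpose is given as keeping participants content with the study and solving problems. Data collection packs are mentioned, with examples in Appendix 3, but the text does not say in which weeks they are filled in.

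**The concern.** The three prototypes, as section 2.0 describes them, act at the moment of use: heat and vibration against pain, lights that respond to stretches, and a silent alert to the teacher. Data collected only when the child has no device could miss effects of that kind.

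Use is also a result in its own right. The primary objective in section 4.0 covers how the prototypes are used as well as their impact. Section 5.0 leaves it to participants to decide when to use them, so use will vary between children and over time. If it is not recorded as it happens, it has to be reconstructed afterwards, partly by children as young as 7 (section 6.1).

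The STOP/GO rule in section 9.0 depends on the share reporting a positive change in condition management (50%, 30% and 10%). The protocol does not say whether that answer refers to life with the device or to life after its return. A schedule that collects data only off device makes this ambiguity more important.

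**Working it through.** No formula for sample size, power or alpha is involved, and the plan gives no figure to reproduce. The check lays the steps out in order and compares them with the stated comparison.

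**Step 1: device status in each step**

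| Step | Length | Child has the Toolbox at home or school? | Data collection named? |
|---|---|---|---|
| 5.3 Baseline | 2 weeks | No | Yes |
| 5.4 Prototype training | 1 to 1.5 hours | Training session only | No |
| 5.5 Use of prototypes | 3 months | Yes | No |
| 5.6 Return | not stated | Handed back | No |
| 5.7 Post-intervention | 2 weeks | No | Yes |
| 5.8 Interview | 1 hour | No | Yes, looking back on use |

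**Step 2: overlap of collection with use**

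- Period of use: section 5.0 places it in August, September and October, so 31 + 30 + 31 = 92 days, and 92 / 7 = 13.1 weeks.
- Labelled data collection periods: 2 + 2 = 4 weeks.
- Overlap of those 4 weeks with the 13.1 weeks of use: 0 weeks.

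**Step 3: recall span at the interview**

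This assumes the steps run in listed order without gaps.

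- Most recent use: at least 2 weeks before the interview, because 5.7 lies between return and interview.
- Earliest use: 92 + 14 = 106 days, and 106 / 7 = 15.1 weeks, or about 3.5 months.
- Any delay in arranging interviews lengthens both figures.

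**Step 4: does any other text supply in-use data?**

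- Weekly check-ins: sections 5.0 and 11.0 both describe troubleshooting, and neither describes recording data.
- Interview: section 5.0 gives it a separate purpose (usability, wider impact on life, ideas for future outcome measures), and it comes after return.
- Packs: no timing during step 5.5 is given in the text.

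The body of the protocol therefore promises in-use data in three places and schedules none.

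**The case against.** The case on the other side has four parts.

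First, three sections state an intention to collect in-use data. The step list consists of one-line headings, and step 5.5 is silent rather than negative. Families are trained in data collection at step 5.2, before baseline, so the packs might run through the period of use. The design figure (Appendix 2) and the packs (Appendix 3) are not available here and could settle this. This part stands. A reader might infer that the stated comparison cannot be made at all, and the documents do not show that.

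Second, a reader might take step 5.7 as the only source of data after baseline. It is not, because the interview at 5.8 is another. The interview does not close the gap, since it also follows return and looks back.

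Third, the protocol aims at some effects that could outlast use: self-management skills and physiotherapy engagement (section 4.0), the relationship with the teacher (section 5.0), lasting health behaviours (section 2.0), and less pain in the long term through better physiotherapy compliance (section 3.0). A reader might infer that an effective device would show no change between 5.3 and 5.7. That would follow only if all benefit ended with return, which the protocol does not say. For the lasting effects, step 5.7 is informative.

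Fourth, this is a qualitative feasibility study that looks for indications of impact, and the STOP/GO question can be answered at interview. Recall limits such an answer without making it worthless. This lowers the weight of the point but does not remove it: section 5.0 names a particular comparison, and the schedule beneath it lists no prospective data for one of its two sides.

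**Conclusion.** The concern holds as a mismatch between what section 5.0 says will be compared and what its step list schedules. Both labelled periods, 4 weeks in total, fall when the child has no device, and none of the roughly 13 weeks of use has a listed collection period. Followed as written, prospective data would compare off device with off device. Effects that occur mainly during use could be missed, or would rest on recall over up to about 3.5 months.

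This rests on two assumptions: that the steps run in the listed order, and that the body text is the full schedule. If an appendix does schedule in-use collection, the remaining defect is that section 5.0 omits the data its own comparison relies on. If none does, the comparison has no prospective in-use side. The text needs correcting in either case, and before step 5.5 begins, because in-use data not recorded at the time cannot be recovered later.

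**What to change.** In section 5.0:

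1. Schedule a data collection period inside step 5.5, before return at 5.6, with the same pack as at baseline. The last two weeks are one option, provided they fall in school term so that the classroom device is covered.
2. Name this as the in-use period that is compared with baseline.
3. Log prototype use at each existing weekly check-in. A single window near the end cannot supply the use data over three months that section 15.0 promises; the weekly log can, and it also covers August, before the school context begins.
4. Keep step 5.7 as a separate off-device follow-up and state what it is for, for example whether any benefit lasts after return.
5. If an appendix already sets in-use collection, state its timing and instrument in section 5.0.

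If no in-use data will be collected, restate the comparison as baseline versus post-return, and withdraw the in-use claims in sections 3.0, 5.0 and 15.0.

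The cost is at most one extra two-week pack per family and brief logging at contacts that already take place. This assumes that the baseline pack can be reused unchanged; the pack itself was not available to check.

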6.1 Selection of Participants

Inclusion Criteria

- Aged 7- 16 years (minimum age is 7 to ensure participants can adequately engage with the prototypes and describe their experience)
- Diagnosis of JIA
- Currently experiencing JIA symptoms
- Currently managed within SCH Rheumatology Service
- Fluent in verbal and written English
- Access to a computer with an internet connection to facilitate virtual co-design workshops due to the COVID-19 pandemic

Exclusion Criteria

- Aged <7 years or >16 years
- Non-fluent in verbal and written English
- Diagnosis of autistic spectrum disorder (ASD)
- Children with medically unexplained pain, pain amplification syndromes or other pain disorder
- Co-existing joint or muscle disorder other than JIA

We have excluded CYP with ASD because it can affect sensory processing including the interpretation of pain and may also affect how CYP are able to communicate. We have excluded CYP with other pain disorders because this would likely behave and respond differently to pain associated with JIA. We have excluded CYP with any co-existing joint or muscle disorder other than JIA because these may behave or respond differently to symptoms associated with JIA.

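### Section 5.0 judges impact by baseline against in-use data and gives the second device-free period (5.7) no role, so change over time can be read as device impact

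*Protocol*

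**What the plan says.** Section 5.0 (Study Design) states that the potential impact of the devices is assessed by "comparing baseline qualitative data about living with JIA, with data collected when the devices are in use". It names no other period for this comparison.

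The WP5 schedule in the same section lists, in order:

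- "5.3 Baseline data collection period (2 weeks")
- "5.5 Intervention period using prototypes (3 months")
- "5.6 'JIA Toolbox' returned to SCH"
- "5.7 post-intervention data collection period (2 weeks")

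Item 5.7 therefore falls after the devices have gone back. It is separate from the closing interview, which is item 5.8.

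Section 3.0 describes the data more loosely, as "experiences of living with JIA both with and without" the Toolbox, without saying which periods are set against each other. WP6 item 6.1 says only that the qualitative data are analysed with the healthcare professionals in the team.

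Two further statements bear on change over time. The inclusion criteria in Section 6.1 require "Currently experiencing JIA symptoms". Section 5.0 says that the intervention period "will take place over August, September and October, giving CYP 1 month to get used to the devices prior to using them in a school" setting.

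**The concern.** The schedule runs device-free, with devices, device-free again. The stated comparison uses the first two of these periods only. In a single group, a before-against-during comparison cannot separate what the devices did from what would have happened anyway.

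The protocol's own terms make such change plausible. Children who enter because they currently have symptoms will on average tend to improve. The in-use months also start in the summer holiday and run into the new school year, which may alter symptoms, activity and contact with teachers in either direction.

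What is at stake is interpretation; no test or error rate is involved. The protocol still intends to use the results as evidence of effectiveness and viability in support of further funding (Sections 3.0 and 15.0). Families are also asked for two weeks of post-return data that the stated comparison does not use.

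**Working it through.** The protocol gives no figure on this point, so there is none to reproduce. The check follows from the schedule, with a device effect of zero throughout.

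**Inputs from the protocol:** baseline 2 weeks (5.3), use 3 months (5.5), post-return data 2 weeks (5.7), use in August to October.

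**Assumptions:** 3 months is taken as 13 weeks; data are spread evenly within each period; periods are contiguous unless stated. The trend shapes are illustrative.

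**Timeline in weeks from the start of baseline:** baseline 0 to 2 (midpoint 1), use 2 to 15 (midpoint 8.5), post-return 15 to 17 (midpoint 16).

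**Comparisons:**
- A, as written: in-use mean minus baseline mean.
- B: in-use mean minus the average of the two device-free means.

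**1. Steady drift of 1 unit per week**
- A = 8.5 − 1 = 7.5 units.
- B = 8.5 − (1 + 16)/2 = 0.
- With a 2-week gap before use only, the midpoints are 1, 10.5 and 18: A = 9.5 and B = 10.5 − 9.5 = +1.
- With a 2-week gap after use only, the midpoints are 1, 8.5 and 18: A = 7.5 and B = 8.5 − 9.5 = −1.

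**2. Regression to the mean**, taken as 1 − exp(−t/τ), with an eventual shift of 1. The mean over a period from a to b is 1 − τ[exp(−a/τ) − exp(−b/τ)]/(b − a). For τ = 4 weeks the period means are 0.213, 0.821 and 0.981, so A = 0.821 − 0.213 = 0.608 and B = 0.821 − (0.213 + 0.981)/2, about 0.22.

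| τ (weeks) | A | B | B/A |
|---|---|---|---|
| 2 | 0.576 | 0.260 | 0.45 |
| 4 | 0.608 | 0.223 | 0.37 |
| 8 | 0.500 | 0.125 | 0.25 |

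Using both device-free periods cuts the spurious change by roughly half to three quarters but does not remove it.

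**3. A step of size 1 on return to school**, placed at 1 September, with the post-return period in term. Two of the three in-use months follow the step, so the in-use mean is 2/3.
- Baseline in the holiday (0): A = 2/3 − 0 = 0.67; B = 2/3 − (0 + 1)/2 = 0.17.
- Baseline in term (1): A = 2/3 − 1 = −0.33; B = 2/3 − (1 + 1)/2 = −0.33.

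The protocol does not say whether baseline falls in term or holiday, so comparison B cannot be relied on to deal with the school calendar.

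**The case against.** The strongest reply is that the protocol never says that only baseline and in-use data will be compared. Section 3.0 speaks of experience with and without the Toolbox, item 5.7 is a period without it, and an analysis plan that is not shown may use it. This stands in part: there is no express exclusion of 5.7. But Section 3.0 does not name the periods compared, whereas Section 5.0 does, and it names baseline alone. The point concerns a comparison that the protocol states too narrowly, not detail left to another document.

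A second reply is that this is exploratory qualitative work. That limits the harm to interpretation. It does not remove it, because the protocol also speaks of testing effectiveness, and asking whether a described benefit faded after return suits qualitative data well.

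A third reply is that lasting skills, physiotherapy engagement and positive health behaviours are intended results (Sections 2.0 and 4.0), so persistence after return may be success. This stands. A reader might infer that only children whose gains fade count as evidence for the devices. The documents do not support that rule, and fading in the last two weeks could itself reflect a flare or the school calendar.

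A reader might also infer that 5.7 is the only protection against time trends. That is too strong: use-pattern data let change be set against actual use, and the interviews explore perceived impact. Both are weak safeguards, and neither supplies a second device-free comparison.

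**Conclusion.** The concern holds as a weakness in the stated impact comparison that is cheap to correct. As written, about 7.5 weeks separate the midpoints of the two periods compared, given contiguous periods, 13 weeks of use and evenly spread data. Change over that interval would be read as device impact.

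Bringing in 5.7 helps within limits. Steady drift is removed if the periods are contiguous; a 2-week gap on one side leaves one week's worth of drift, in either direction. Regression to the mean is lessened: under the assumed time constants of 2 to 8 weeks, the spurious part falls from 0.50–0.61 to 0.13–0.26 of the eventual shift. A school-calendar step is not reliably removed.

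Two stronger readings should be resisted. A reader might want to express the bias in points on a symptom scale, but the protocol gives neither such a scale nor a natural rate of improvement, so only the time separation can be stated. A reader might also infer that the change would safeguard the decision to proceed. It would not: the STOP/GO rule in Section 9.0 rests on the share of participants who report a positive change, and that remains open to the same time trends.

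**What to change.** In Section 5.0 and WP6 item 6.1, state that in-use data are compared within each child with both device-free periods, 5.3 and 5.7, on items common to both. The data collection packs are not shown, so confirm that such items exist.

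Report for each child whether a described benefit faded or persisted after return. Read fading as more consistent with a device effect, and persistence as compatible with either lasting skills or natural course. Describe the results as change over time, not as proven effect. Say plainly that the school calendar remains an alternative explanation and that the STOP/GO rule is not protected by this comparison.

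The cost is wording and some analysis time. Both device-free periods are already scheduled, so no new visits, participants or data periods are needed, provided that the packs share items. The downside is that carry-over of learned skills can make the comparison understate impact, which is why persistence is reported separately and not counted against the devices.
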